Evaluation of the effect of the “Eat Less Meat” one-month challenge on meat consumption among French university students

Date: January 31st, 2023

Principal Investigator: [name]

Description:

In a context where meat consumption should be dramatically reduced in western countries to improve both population and planet health, the “Eat Less Meat” one-month challenge is a new behavioural intervention that aims (i) to weaken meat consumption habit and (ii) to enhance intrinsic motivation to eat less meat to trigger long-term reduction in meat consumption. The present registration focusses on the quantitative evaluation of the effect of this challenge on university student’s meat consumption.

STUDY INFORMATION

Hypotheses

Main hypothesis:

H1: The “Eat Less Meat” challenge will have decreased meat consumption in participants during the challenge and 3 months after challenge completion compared to before.

Secondary hypotheses:

H2: The “Eat Less Meat” challenge will have increased (resp. decreased) nutritional quality (resp. environmental impact) of the diet in participants during the challenge and 3 months after challenge completion compared to before.

H3: The “Eat Less Meat” challenge will have weakened meat consumption habits in participants during the challenge and 3 months after challenge completion compared to before.

H4: The “Eat Less Meat” challenge will have increased health, ethics and animal welfare motivations for food choices in participants during the challenge and 3 months after challenge completion compared to before.

Study design

Parallel two-arm randomized controlled trial with repeated measures (online questionnaires) pre-, during- and post-intervention. All the participants will be recruited to take part in the “Eat Less Meat” challenge for one month. Participants in the control group will take part in the challenge 3 months after the participants in the intervention group. Participants in both groups will complete the online questionnaires at the exact same time, i.e., pre-, during- and post-intervention measures will take place before the control group starts the challenge. A figure summarizing the study design is available in **Appendix 1**.

Randomization

A 1:1 randomisation sequence will be generated before recruitment using the Random Allocation software¹ to allocate each participant to one of the experimental arm (control or intervention).

SAMPLING PLAN

Data collection procedures

¹ Mahmood Saghaei, ‘Random Allocation Software for Parallel Group Randomized Trials’, *BMC Medical Research Methodology*, 4 (2004), 1–6 <<https://doi.org/10.1186/1471-2288-4-26>>.

Inclusion criteria.

- Aged ≥ 18
- BMI ≥ 18.5
- University student in 'Bourgogne Franche-Comté'
- Fluent in French
- Available email address
- Available Instagram profile
- Not vegetarian or vegan or pescatarian
- Not pregnant/breastfeeding
- No iron deficiency

Brief description of the "Eat Less Meat" challenge.

Participants will be recruited through social media, emails, flyers and posters on campus to take part in the "Eat Less Meat" challenge; recruitment materials will mention that the challenge is part of a research study. Eligible participants that will give their informed consent will be able to choose their goal for the challenge for one month: (i) no meat, (ii) meat 3 times a week, (iii) meat 6 times a week (which will need to be lower than current consumption) and will be enrolled in the challenge. The 'meat category' includes all red meat and poultry but not fish or other animal-sourced food products (eggs, dairy, etc.). The first day of the challenge, the participants will receive by email a cookbook of easy-to-prepare and cheap meat-free recipes and a starter kit with advices and motivational tips, then they will receive an email each week with more advices and motivational tips. Participants will be also asked to follow the Instagram account of the challenge where during one month (i) one post will be posted each day, (ii) engaging stories requiring interactions will be posted regularly, (iii) participants can ask their questions to the research team, (iv) participants can interact with each other's. The Instagram posts will cover three main topics: (i) knowledge about meat and its impact on health and environment, (ii) tips for meat-free cooking, (iii) social/contextual pressure to eat meat and how to avoid it. Emails and posts will aim at keeping the participants engaged in the one-month challenge and to enhance their intrinsic motivation to eat less meat.

Data collection for evaluation.

Eligible participants will be informed that their participation will involve completing a first online questionnaire on sociodemographics at the point of inclusion (10 min) and then three other online questionnaires at three time points: pre-, during- and post-intervention (30 min each time, 10€ compensation).

Sample size

As a minimum, we will aim to recruit 200 university students willing to take part in the challenge but we will include in the study all voluntary students that will register. Registrations will close the day before the challenge starts for the intervention group.

Sample size rationale

The sample size was determined based on a power analysis (GPower v3.1) to detect a small effect size of $f=0.10$ for a within-between interaction in a mixed model with 3 repeated measures. A total sample size of 164 participants was necessary to reach 0.80 power at 0.05 alpha. Considering an attrition rate in between 15 and 20%, we will aim to recruit 200 university students willing to take part in the challenge.

VARIABLES

Manipulated variables

We will manipulate whether participants will be assigned to intervention or control group (challenge 3 months after the intervention group). It will be coded as a binary variable: 'intervention' or 'control' at the participant level.

Measured variables

The sociodemographics questionnaire will record age, gender, scholarship status, educational level, field, parents' educational level, place of living, dieting status and type of diet.

The evaluation questionnaires will record three types of variables at the three time points:

- Food consumption frequency

The food frequency questionnaire (FFQ) will include 109 foods, 12 non-alcoholic drinks and 4 alcoholic drinks with frequency assessed by a 6-item scale from "Never" to "Several times a day"². Participants will estimate their usual portion size for 75 food items using photos on a 5-point scale derived from the SU.VI.MAX portion book³. For the 50 remaining food items, we will use the standard portion size. Consumption frequencies of each item will be transformed into daily frequencies and daily intake will be calculated by multiplying the daily frequency by the estimated portion size. Individual nutrients intake will then be calculated for all the participants before and during the lockdown by multiplying the daily intake of each food item by the nutritional values from the SU.VI.MAX nutrient composition database⁴. Participants will be asked about their food consumption for the month before questionnaire completion, i.e., the month before the challenge, the month of the challenge and the third month after the challenge for the intervention group (all the measures will take place before the control group start the challenge).

- Meat consumption habit

The strength of meat consumption habit will be assessed using the Self-Report Habit questionnaire⁵ including 12 items accompanied by a 6-point response scale anchored by 'strongly disagree' and 'strongly agree' from 1 to 6. The scores will be coded such that high values indicated strong habits. Participants will be asked about their meat consumption habit at the time of questionnaire completion.

- Food choice motives

The food choice questionnaire (FCQ) will be the adapted French version of the Food Choice Questionnaire⁶. It includes 30 items and 10 subscales: health, mood, convenience, sensory appeal, natural content, price, weight control, familiarity, ethical concern and animal welfare. Answers to each item will range from 1 to 4: 1 = Not at all important; 2 = A little important; 3

² Manik Kadawathagedara and others, 'Diet during Pregnancy: Influence of Social Characteristics and Migration in the ELFE Cohort', *Maternal and Child Nutrition*, 17.3 (2021), 1–13 <<https://doi.org/10.1111/mcn.13140>>.

³ S Hercberg, M Deheeger, and P Preziosi, *SU.VI.MAX. Portions Alimentaires : Manuel Photos Pour l'estimation Des Quantités*, Economica (Paris, 2002).

⁴ S Hercberg, *Table de Composition Des Aliments SU.VI.MAX*, Economica (Paris, 2006).

⁵ Bas Verplanken and Sheina Orbell, 'Reflections on Past Behavior: A Self-Report Index of Habit Strength', *Journal of Applied Social Psychology*, 33.6 (2003), 1313–30 <<https://doi.org/10.1111/j.1559-1816.2003.tb01951.x>>.

⁶ Muriel C.D. Verain and others, 'Sustainable Food Choice Motives: The Development and Cross-Country Validation of the Sustainable Food Choice Questionnaire (SUS-FCQ)', *Food Quality and Preference*, 93 (2021), 104267 <<https://doi.org/10.1016/j.foodqual.2021.104267>>; [name] and others, 'Food Choice Motives and the Nutritional Quality of Diet during the COVID-19 Lockdown in France', *Appetite*, 157 (2021), 105005 <<https://doi.org/10.1016/j.appet.2020.105005>>.

= Moderately important; 4 = Very important. Participants will be asked about their food choice motives for the month before questionnaire completion.

Indices

Three scores will be calculated based on the FFQ at each time point:

- **Meat consumption.** Meat daily intake (in grams) will be calculated by summing daily intake for all the items of the FFQ that fall into the meat category.
- **Nutritional quality.** Adherence to the French dietary guidelines will be evaluated using the simplified PNNS-GS2⁷. The sPNNS-GS2 builds on the distinction between malus components (less healthy food groups which consumption should be limited, carrying a negative score, i.e., red meat, processed meat, sugary foods, sweet-tasting beverages, alcoholic beverages, salt) and bonus components (healthier food groups carrying a positive score, i.e., fruits and vegetables, nuts, legumes, whole-grain food, milk and dairy products, fish and seafood) reflecting established knowledge on the relationship between food groups consumption and non-communicable disease risk factors. sPNNS-GS2 will be computed for each participant with slight modifications to the calculation compared to the initial definition (range: -17 to 11.5) as in previous research⁸.
- **Environmental impact.** Greenhouse gas emissions (GHGEs) will be derived from the French food environmental impact data- base Agribalyse 3.0 drawn up by the French Agency for Ecological Transition that includes GHGEs values for 2480 food items (ADEME, 2020), based on Life Cycle Analyses of food products. The items of the food frequency questionnaire will be associated to all the corresponding food items from Agribalyse 3.0. GHGEs of each item of the food frequency questionnaire will be calculated as the average GHGEs of individual foods from Agribalyse 3.0 associated to each item. GHGEs of participants' daily diets will be calculated by multiplying the daily intake of each food item by its associated GHGEs per kg.

One score will be calculated based on the Self-Report Habit questionnaire at each time point:

- The Self-Report Habit Index will be computed by averaging ratings for all the individual items in the questionnaire.

Ten scores will be calculated based on the FCQ at each time point:

- A score for each subscale will be computed by averaging ratings for the three individual items in each of the ten subscales.

ANALYSIS PLAN

Statistical models

We will use linear mixed models to investigate whether changes in measured variables pre- (T0), during- (T1) and post-challenge (T2) differ significantly between participants in the intervention and the control group.

We will run linear mixed models with meat consumption (H1), nutritional quality (H2), environmental impact (H2), Self-Report Habit Index (H3), health motives (H4), ethics motives

⁷ Chaltiel and others, 'Programme National Nutrition Santé - Guidelines Score 2 (Pnns-Gs2): Development and Validation of a Diet Quality Score Reflecting the 2017 French Dietary Guidelines', *British Journal of Nutrition*, 122.3 (2019), 331–42 <<https://doi.org/10.1017/S0007114519001181>>.

⁸ [name] and others, 'Food Choice Motives and the Nutritional Quality of Diet during the COVID-19 Lockdown in France', *Appetite*, 157.105005 (2021) <<https://doi.org/10.1016/j.appet.2020.105005>>.

(H4) and animal welfare motives (H4), as dependant variables, time (T0, T1 / T0, T2), group (intervention, control), time*group interaction as fixed effects and participant as random effect. These models will be adjusted for gender, age and BMI in order to control for potential confounding effects. We will report adjusted mean differences between T1 and T0, and between T2 and T0 for the intervention and the control group.

If we find a significant effect of the intervention on meat consumption, i.e., time*group interaction is significant in the models above, we will run two additional models on the intervention group only to investigate whether the level of the challenge (i.e., (i) no meat, (ii) meat 3 times a week, (iii) meat 6 times a week) differentially influence meat consumption reduction. The first linear mixed model will be run with meat consumption as dependant variable, time (T0, T1 / T0, T2), level (i, ii, iii), time*level interaction as fixed effects and participant as random effect. We will report adjusted mean differences between T1 and T0, and between T2 and T0 for each level. In the second linear mixed model, we will substitute the level of the challenge by the difference between baseline meat consumption frequency (in times per week) and the level of the challenge (continuous variable).

All statistical analyses will be performed using SAS version 9.4 (SAS Institute, Inc., 2012 SAS® 9.4. Cary, NC). The proc mixed will be used for mixed models. The level of significance will be set at $p < 0.05$ for all pre-registered analyses.

Data exclusion

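### Does the 3-month lag between arms put the control group's own challenge month inside its T2 recall window?

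*Combined protocol and SAP*

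**What the plan says.** Four statements in the combined protocol and SAP bear on the timing.

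- **The lag.** Study design: "Participants in the control group will take part in the challenge 3 months after the participants in the intervention group". Manipulated variables repeats it in brief: "intervention or control group (challenge 3 months after the intervention group". Neither place gives a reference point.
- **The length of the challenge.** In the description under Data collection procedures, participants "choose their goal for the challenge for one month".
- **The timing of T2.** Each of H1 to H4 concerns change "during the challenge and 3 months after challenge completion compared to before". Measured variables sets the three recall periods of the food frequency questionnaire as "the month before the challenge, the month of the challenge and the third month after the challenge for the intervention group".
- **The order of events.** Study design: "Participants in both groups will complete the online questionnaires at the exact same time", and "pre-, during- and post-intervention measures will take place before the control group starts the challenge". Measured variables repeats the order in the same sentence that defines the T2 period: "the third month after the challenge for the intervention group (all the measures will take place before the control group start the challenge".

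Study design also refers the reader to a figure in Appendix 1. That figure is missing from the text available here, which is not a fault of the plan.

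**The concern.** The sentence on the lag compares one group taking part with the other group taking part, so a start-to-start reading comes naturally. On that reading the control group would begin at month 3, before T2 has been collected. Its T2 recall month would then be its own challenge month.

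The stakes would be high if this happened. The T0 to T2 time-by-group interaction tests the 3-month part of all four hypotheses, including the main one. With both groups treated in or before the T2 window, that interaction would no longer estimate the effect of the challenge, and no adjustment in the planned mixed models would recover it.

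**Working it through.** The plan's one computed figure, the total sample size of 164, does not enter this question. The check is calendar arithmetic, in months from the start of the intervention group's challenge.

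**Inputs**

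- Challenge length D = 1 month (Data collection procedures).
- T2 recall = third month after the challenge (Measured variables).
- Lag = 3 months, reference point not stated (Study design, Manipulated variables).
- Same questionnaire dates in both groups (Study design).
- All measures before the control start (Study design, Measured variables).

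**T2 window**

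- Intervention challenge: 0 to D = 0 to 1.
- T2 recall: D + 2 to D + 3 = 3 to 4.
- Earliest T2 completion: D + 3 = 4, which matches the 3 months after completion in H1 to H4.

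**Control challenge under each reading**

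| Lag counted from | Control challenge | Overlap with T2 recall (3 to 4) | T2 no later than control start? |
|---|---|---|---|
| Intervention start | 3 to 4 | 1 month (all of it) | No: 4 > 3 |
| Intervention completion | 1 + 3 = 4 to 5 | 0 | Yes: 4 ≤ 4 |

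The start-to-start reading breaks the ordering rule. The completion reading is compatible with every statement.

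**Size of the error if the excluded schedule were followed.** Let E be the effect in the challenge month and w the share of it that persists to the third month afterwards. Assume that both groups respond alike.

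- Intended T2 contrast: wE − 0 = wE.
- Contrast with the control group in its challenge month: wE − E = (w − 1)E.
- At w = 1: intended E, obtained 0.
- At w = 0.5: intended 0.5E, obtained −0.5E.

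The plan gives no value for w; these two are illustrations.

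**T1.** The T1 recall period is months 0 to 1 and the control group starts at month 3 at the earliest. The T0 to T1 contrast is therefore clean on either reading.

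**The case for a change.** The strongest case for a change is that even the completion reading leaves no slack. T2 recalls the full third month, so it cannot be completed before month 4, and the control group starts at month 4. The plan aims to collect a 30-minute questionnaire from at least 200 students, and the readable text gives no response window and no rule for late answers. Food recall covers the month before completion, so a control answer given 7 days after the start would carry 7/30, about 23%, of its window into the challenge. The habit index refers to the moment of completion, so a late control answer would come after the starter kit has arrived.

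The arithmetic stands, but its premises are weak. It takes a lag given in whole months as exact to the day, although the readable text sets no calendar dates. It also supposes T2 answers after the control start, which the ordering rule does not allow. If T2 collection closes before the control group begins, an unanswered questionnaire is simply missing, and the plan covers that: the models use all available data, with multiple imputation as a sensitivity analysis.

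It is also fair to say that a reader who saw only the lag sentence could schedule the control group too early. In Study design, however, the ordering rule comes almost directly after that sentence, so such a reader is unlikely.

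**Conclusion.** The concern does not call for a change. The start-to-start arithmetic is correct, and the lag does lack a stated reference point. A schedule that put the control challenge in the T2 window would nevertheless contravene a rule that the plan states twice. Counted from completion, the overlap falls from one full month to zero and all statements agree. A zero or reversed T2 contrast is therefore the consequence of a schedule that the plan forbids, not of the plan as a whole.

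This is a gap that the study team fills by following its own ordering rule. Restating that rule would change no estimate, test or sample size. The conclusion rests on two assumptions: that the ordering rule is followed in practice, and that the Appendix 1 figure does not contradict the text. If that figure showed the control group starting at month 3, the passages would have to be reconciled and the T2 comparison looked at again.

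### The plan does not settle whether each outcome gets two pairwise mixed models or one three-time model, and a participant random effect has a modest, cheaply removed weakness either way

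*Combined protocol and SAP*

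**What the plan says.** Under Analysis plan, Statistical models, each outcome is modelled with time (written as T0, T1 / T0, T2), group and "time*group interaction as fixed effects and participant as random effect", adjusted for gender, age and BMI and fitted in SAS PROC MIXED. No REPEATED statement or covariance type is named. On reporting: "We will report adjusted mean differences between T1 and T0, and between T2 and T0 for the intervention and the control group". An effect on meat consumption is declared if "time*group interaction is significant in the models above".

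The text points two ways on how many times enter a model:

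- **Two pairwise fits.** The slash in the time factor separates T0 with T1 from T0 with T2, and the reported differences are exactly those two.
- **One three-time fit.** Sample size rationale powers the trial "for a within-between interaction in a mixed model with 3 repeated measures". The challenge-level analysis uses the same slash notation but calls its model a single first model, from which both differences are reported.

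The Missing data section bases the mixed models on all available data points and adds multiple imputation as a sensitivity analysis, without saying which variables the imputation model contains. Sample size rationale allows for 15 to 20% attrition.

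**The concern.** The T2 comparison carries the three-month claim in H1 to H4, so its estimate and standard error should not depend on an unstated modelling choice.

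A random intercept fitted to three times gives one variance and one correlation for all times, so both contrasts get the same standard error whatever their real precision. The recall periods (month before, challenge month, third month after) are unevenly spaced and one of them is the intervention itself, so there is no reason to expect equal correlations.

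A pairwise T0/T2 fit avoids that, but a participant who answers at T1 and is lost by T2 then contributes nothing learned during the challenge. People who fail the challenge month may well be the ones who stop answering.

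**Working it through.** **Inputs from the documents.** f = 0.10, 3 measures, power 0.80, alpha 0.05, total N = 164, attrition 15 to 20%, recruitment target 200, 1:1 allocation (so 82 per arm at N = 164). The documents give no SD or correlation at any time; all those below are assumptions. Correlations are listed as T0-T1 / T0-T2 / T1-T2, with SD 1 at each time unless stated.

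**1. The plan's own figure.** For the within-between interaction, λ = f²·N·m/(1−ρ), with df₁ = m−1 and df₂ = (N−2)(m−1). With m = 3 and assumed ρ = 0.5, N = 164 gives λ = 0.01·164·3/0.5 = 9.84 on 2 and 324 df, power 0.805; N = 162 gives 0.7998. The stated 164 reproduces. With m = 2 and the same f and ρ, N = 200 completers are needed (λ = 0.01·200·2/0.5 = 8.0, power 0.804). The number of times in the model therefore matters to the power basis.

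**2. Pairwise reading, standard errors.** With two times, the random-intercept residual variance is half the pooled variance of the change score (given positive within-person covariance). The time-by-group standard error is then the correct √[(2/n)(V₀+Vⱼ−2Cov₀ⱼ)]. At 0.6/0.4/0.5 and n = 82:

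- T1: √[(2/82)·0.8] = 0.1397
- T2: √[(2/82)·1.2] = 0.1711

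Model/true ratios are 1.000 in all ten covariance scenarios tried. Simulated type I error (1,500 trials) is 0.055 at T1 and 0.049 at T2 with complete data, and 0.049 and 0.047 with about 9% and 18% missing at T1 and T2.

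**3. Pairwise reading, dropout.** Assume 20% of the intervention arm is lost by T2, with log-odds of loss linear in T1 meat intake and no such selection in controls. Predict the intervention arm's T2 mean from completers, using T0 only and then T0 with T1 (2,000,000 simulated participants):

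| Correlations | Odds per SD of T1 | Bias, T0 only (SD) | Bias, T0 and T1 (SD) |
|---|---|---|---|
| 0.7/0.5/0.6 | 2 | −0.034 | about 0 |
| 0.7/0.5/0.6 | 3 | −0.050 | about 0 |
| 0.6/0.4/0.5 | 2 | −0.034 | about 0 |
| 0.6/0.4/0.5 | 3 | −0.051 | about 0 |
| 0.6/0.5/0.6 | 2 | −0.039 | about 0 |
| 0.6/0.5/0.6 | 3 | −0.058 | about 0 |

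Negative means intake looks lower than it is, which favours the intervention. With a T0-T2 correlation of 0.5 the T2 standard error is √[(2/82)·1.0] = 0.156, so the bias at that correlation is 0.034/0.156 = 0.22 to 0.058/0.156 = 0.37 of a standard error.

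**4. Three-time reading.** Let D₀₁, D₀₂, D₁₂ be the variances of the pairwise differences and D̄ their mean. Compound symmetry uses D̄ for every contrast, so model SE/true SE = √(D̄/D₀ⱼ).

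| Scenario | D₀₁, D₀₂, D₁₂ | D̄ | T1 ratio (type I) | T2 ratio (type I) |
|---|---|---|---|---|
| 0.7/0.5/0.6 | 0.6, 1.0, 0.8 | 0.80 | 1.155 (2.4%) | 0.894 (8.0%) |
| 0.6/0.4/0.5 | 0.8, 1.2, 1.0 | 1.00 | 1.118 (2.8%) | 0.913 (7.4%) |
| 0.6/0.5/0.6 | 0.8, 1.0, 0.8 | 0.867 | 1.041 (4.1%) | 0.931 (6.8%) |
| 0.4/0.6/0.5 | 1.2, 0.8, 1.0 | 1.00 | 0.913 (7.4%) | 1.118 (2.8%) |
| all 0.5, T1 SD 1.3 | 1.39, 1.0, 1.39 | 1.26 | 0.952 (6.2%) | 1.122 (2.8%) |
| 0.6/0.4/0.5, T1 SD 1.4 | 1.28, 1.2, 1.56 | 1.347 | 1.026 (4.4%) | 1.059 (3.8%) |
| all 0.5 | 1.0, 1.0, 1.0 | 1.00 | 1.000 (5.0%) | 1.000 (5.0%) |

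Whenever D₀₁ and D₀₂ differ, one common D̄ cannot fit both, so at least one contrast is misstated. Usually one standard error is too small and the other too large; in the sixth row both are too large. The 2-df interaction test stays near nominal, at about 5.5% or less in these settings.

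**The case against.** A reader might infer that the T2 standard error is simply too small and the T1 one too large. The documents do not support that. The time factor as written most naturally describes two pairwise fits, in which a random intercept forces no equality across three correlations and the standard errors are right. Even in a three-time model the direction needs a more variable change at T2 than at T1. Wider spacing in time suggests that, but a month under an imposed goal could make T1 the atypical time, and the fourth and fifth rows of the second table then reverse the pattern. In a three-time model the test that the plan uses to declare an effect would also be the 2-df interaction, which is barely disturbed. All of this stands.

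On dropout, the other side can say that the plan expects little missing outcome data, that multiple imputation is planned, and that the bias rests on assumed selection in one arm only and is well under half a standard error. That limits the size but does not remove the point. The plan's own attrition allowance is 15 to 20%, imputation is a sensitivity analysis rather than the main one, and its model is not stated to include T1. The joint model's freedom from bias is likewise conditional: it holds because the assumed loss depends on observed T1 values.

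**Conclusion.** The point holds as a cheap improvement, with moderate confidence. The plan should say which model it fits, and each reading has a weakness that one specification removes.

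- **Pairwise (more natural):** standard errors are sound with complete data. The T2 effect is open to a bias of about 0.03 to 0.06 SD towards the intervention, assuming 20% loss confined to that arm and a 2- to 3-fold rise in odds per SD of T1 meat intake.
- **Three-time:** single-contrast standard errors are off by about 4 to 15% under the unequal correlations assumed here with equal SDs, in a direction that the documents do not fix. The interaction test is only mildly affected.

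None of this shows that the plan as worded gives wrong inference.

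**What to change.** State that each outcome is analysed in one model containing T0, T1 and T2. Replace the random participant effect by REPEATED time / SUBJECT=participant TYPE=UN, with DDFM=KR, and take both between-arm contrasts (T1−T0 and T2−T0) from that model. This lets each contrast have its own variance, uses T1 for participants lost by T2, and agrees with the three-measure power analysis. If pairwise fits are kept instead, say so, reconcile them with that power analysis, and state that the imputation model includes T1.

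The cost is a sentence of plan text and one SAS statement. The covariance parameters rise from 2 to 6, which is negligible with 164 to 200 participants.

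### The level model compares self-chosen goals in the intervention arm alone, so regression to the mean and chooser-specific time trends can pass for a level effect; compare the arms within chosen level and word the result accordingly

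*Combined protocol and SAP*

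**What the plan says.** Only the arm is randomised (Randomization: "A 1:1 randomisation sequence will be generated before recruitment"). The goal is not. Under the brief description of the challenge, consenting participants "will be able to choose their goal for the challenge for one month": no meat, meat 3 times a week or meat 6 times a week. A condition ties the choice to intake: "which will need to be lower than current consumption". It is printed beside the third goal and may be meant for all three.

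Under Statistical models, a significant time-by-group interaction for meat consumption triggers a further step: "we will run two additional models on the intervention group only to investigate whether the level of the challenge" has a differential influence on the reduction. The first model contains time, level, time by level and a random participant effect. The second replaces level with baseline meat frequency minus the chosen level. Adjustment for gender, age and BMI is stated for the main models and not repeated for these two. Both are pre-registered at p < 0.05, and nothing in the plan calls the level result observational.

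On the control arm, Study design says "All the participants will be recruited to take part in the “Eat Less Meat” challenge for one month" and "Participants in the control group will take part in the challenge 3 months after the participants in the intervention group". All three control measurements come before the control group's own challenge.

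**The concern.** The level question is put in causal terms to groups that formed themselves. Someone whose T0 questionnaire happens to read high will tend to read lower at T1 whatever the goal. If people with high reported intake favour one goal and people with low reported intake another, the levels will show different changes from T0 even if no goal does anything. Season, term dates and repeated questionnaires can add trends that differ between types of chooser. With the intervention arm alone, none of this can be subtracted.

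The second model relates the goal to starting intake but does not remove the problem. Its predictor contains baseline meat frequency, which is closely related to the T0 outcome, so a larger gap goes with a larger fall through regression to the mean.

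At stake is a pre-registered significant result saying that one goal level reduces meat more than another when the data show only who chose it. Making the level models conditional on a significant overall effect gives no protection: a real overall effect opens the gate and leaves the bias between levels in place.

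**Working it through.** **1. The plan's own figure, as the basis for the inputs.** Sample size rationale gives f = 0.10, 3 measures, alpha 0.05, power 0.80 and N = 164. The correlation between measures is not stated; take 0.5. With two groups, λ = f²·N·m/(1 − ρ) = 0.01 × 164 × 3/0.5 = 9.84, on (2 − 1)(3 − 1) = 2 and (164 − 2)(3 − 1) = 324 degrees of freedom. Power is 0.805, and 164 is the smallest even N to reach 0.80, so the figure reproduces. Allowing for attrition, 164/0.85 = 193 and 164/0.80 = 205, which bracket the target of 200. This covers the time-by-group test only. The level models use about 164/2 = 82 people split over three self-chosen levels, and no power is given for them.

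**2. Set-up for the level test.**
- From the plan: 82 per arm, self-chosen goal, change from T0, intervention arm only, alpha 0.05.
- Assumed, because the documents give no figures: T0-T1 correlation ρ = 0.5 (also 0.3 and 0.7); the three levels equally popular; higher reported intake goes with a laxer goal.
- Built in: the goal has no effect, and the challenge has the same effect on everyone.

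Choice is a latent score, s × (T0 intake in SD units) plus other influences with variance 0.98, cut into thirds. Its correlation with T0 intake is r = s/√(s² + 0.98). For s = 0.3, 0.6 and 1.0, r = 0.29, 0.52 and 0.71.

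**3. Expected spurious difference.** The top and bottom thirds of a standard normal variable differ in mean by 6 × 0.3636 = 2.18 SD. Regression to the mean then gives a difference in change between the outer levels of (1 − ρ) × r × 2.18. At ρ = 0.5:
- weak link: 0.5 × 0.29 × 2.18 = 0.32 SD
- moderate link: 0.5 × 0.52 × 2.18 = 0.57 SD
- strong link: 0.5 × 0.71 × 2.18 = 0.77 SD

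The simulated means (3,000 runs each) agree: 0.31, 0.55 and 0.77 SD.

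**4. False rejection at nominal 0.05.**

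| Link of choice to baseline | Intervention-only, ρ = 0.5 | Intervention-only, ρ = 0.7 to 0.3 | Arm by level, all ρ |
|---|---|---|---|
| none | 5% | 5% | 4-5% |
| weak | 16% | 10-22% | 5% |
| moderate | 44% | 28-59% | 5-6% |
| strong | 75% | 52-90% | 5-6% |

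A separate simulation at ρ = 0.5 with its own assumed choice strengths gave 23%, 63% and 89%, again against about 5% for arm by level. The range at ρ = 0.5 is therefore roughly 16% to 89%. These runs contain regression to the mean only; chooser-specific time trends would come on top.

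**5. What the comparator does not cure.** Let motivation drive both goal choice and response, with no effect of the goal itself. The arm-by-level contrast then still shows 0.45 to 0.47 SD and rejects in 18% to 24% of runs (intervention-only: 29% to 43%).

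**6. Price in precision.** Subtracting a control change of similar variance multiplies the standard error of a level contrast by √2 = 1.41. A contrast with 80% power has an expected z of 1.96 + 0.84 = 2.80. Dividing by 1.41 gives 1.98, and power falls to about 51%. The six arm-by-level cells average 164/6 = 27 people, and self-selection will make some smaller.

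**The case against.** The strongest reply is that these models are conditional and secondary. No hypothesis from H1 to H4 concerns the level, and the randomised comparison is untouched. All of that stands, and it sets the weight of the point.

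A second reply is that the proposed model cannot isolate the goal either. That also stands. A reader might infer that bringing in the wait-list arm turns the level comparison into a causal one. It does not: it gives a randomised effect of the challenge within each chosen level, and differences between those effects may still reflect who chose. Only randomised goals would settle that.

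A reader might also infer that the control arm's goals are already recorded and simply ignored. The text supports less. It says "Eligible participants that will give their informed consent will be able to choose their goal for the challenge for one month", and choosing is described together with enrolment, so a choice by everyone at inclusion is implied. It is not stated for controls, who might choose only before their own challenge three months later.

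Nor is the point that choosers of a laxer goal eat more at the start and so lose more grams for the same proportional cut. That follows from measuring the outcome in grams per day, and control subtraction would leave it unchanged.

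Finally, the loss of precision is a real cost. It is a reason to keep the intervention-only model as description. It does not justify a biased test.

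**Conclusion.** The point holds for the level analysis and no further. If reported intake steers the choice of goal, the intervention-only time-by-level test does not keep its 5% level: roughly 16% to 89% false rejection at an assumed correlation of 0.5, against about 5% when the arms are compared within level. The size rests on assumed correlations and choice strengths. The condition that the goal lie below current consumption makes some link likely, but the documents do not show how strong it is; with no link the test is sound in this respect. The causal wording is unsupported under either model. H1 and the other main models are unaffected. This is a minor point on a secondary analysis, worth correcting because the change is cheap.

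**What to change.** 1. State under data collection that every participant, in both arms, chooses and records a goal at inclusion before allocation is revealed.
2. Under Statistical models, make time by group by level, fitted in both arms with all lower-order terms, the test of level. Report the intervention-minus-control difference in change, T1 and T2 against T0, within each chosen level.
3. Keep the intervention-only level model as descriptive. Say that the second model's predictor contains baseline frequency, so its slope is subject to regression to the mean.
4. Replace the statement that level influences reduction with one that the effect of the challenge is reported by self-chosen level, and that differences between levels may reflect who chose them.

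The cost is one item for all participants at inclusion, a few lines of text, and the loss of precision shown above: a standard error about 1.4 times larger and small arm-by-level cells. The plan should say that the level comparison is not powered.
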